Pulmonary toxicity	All pulmonary events	Evaluate thoroughly for other commonly reported etiologies such as pneumonia/infection, lymphangitic carcinomatosis, pulmonary embolism, heart failure, chronic obstructive pulmonary disease (COPD), or pulmonary hypertension.
	Grade 1	
Continue atezolizumab and monitor closely.
 
Re-evaluate on serial imaging.
 
Consider patient referral to a pulmonary specialist.
 
For recurrent pneumonitis, treat as a Grade 3 or 4 event.

	Grade 2	
Hold atezolizumab.
 
Refer patient to pulmonary and infectious disease specialists and consider bronchoscopy or bronchoscopic alveolar lavage (BAL).
 
Initiate treatment with 1–2 mg/kg/day oral prednisone or equivalent.
 
If event resolves to Grade 1 or better within 12 weeks, taper corticosteroids and resume atezolizumab according to the guidelines above.
 
Permanently discontinue atezolizumab if event does not resolve to Grade 1 or better within 12 weeks.
 
For recurrent events, treat as a Grade 3 or 4 event.

AE Management and Dose Interruption Guidelines for Specific Toxicities		
Toxicity	Severity/ Duration	Management
	Grade 3 or 4	Hold atezolizumab. Bronchoscopy or BAL is recommended. Initiate treatment with 1–2 mg/kg/day oral prednisone or equivalent. If event does not improve within 48 hours after initiating corticosteroids, consider adding an immunosuppressive agent. If event resolves to Grade 1 or better, taper corticosteroids over ≥ 1 month. For Grade 3 AEs, patient may only resume treatment after consultation with the Study Chair; for Grade 4, patient cannot resume treatment, regardless of benefit.

8.5 Adverse Event Reporting

Toxicities (including suspected reactions) that meet the expedited reporting criteria as outlined in [Section 16.0](#) of the protocol must be reported to the Operations Office, Study Chair and NCI via CTEP-AERS, and to the IRB per local IRB requirements.

9.0 STUDY CALENDAR

9.1 TREATMENT AND SPECIMEN SUBMISSION

REQUIRED STUDIES	Base-line	WEEK																				Off Tx Prior to HG Recur ≠	After HG Recur #			
		1	4	7	10	13 *	16	19	22	25*	28	31	34	37	40	43	46	49	61	73	85			97	109+	
PHYSICAL																										
History and Physical Exam	X Σ		x	x	X	x	x	x	x	x	x		x		x		x									
Weight and Performance Status	X Σ																									
Toxicity Notation Ω		X	X	X	X	X	X	X	X	X	X	X	X	X	X	X	X	X	X						X Ω	X Ω
Baseline Abnormalities	X																									
Assess pulmonary signs and symptoms α		X	X	X	X	X	X	X	X	X	X	X	X	X	X	X	X	X	X						X Ω	X Ω
Disease Assessment ≠						X				X			X					X	X	X	X	X	X	X q24 wks	X	
LABORATORY																										
CMP/ Serum Chemistry €	X λ	X	X	X	X	X	X	X	X	X	X	X	X	X	X	X	X	X								
CBC w/ diff, platelets β	X λ	X	X	X	X	X	X	X	X	X	X	X	X	X	X	X	X									
Pregnancy test (if applicable) §	X λ																									
TSH ¥	X λ			x		X		x		X		x		X		x		X								

Cal 9.1 continued on next page. Click here for [Footnotes](#):

REQUIRED STUDIES	Base -line	WEEK																				Off Tx Prior to HG Recur #	After HG Recur #		
		1	4	7	10	13 *	16	19	22	25*	28	31	34	37	40	43	46	49	61	73	85			97	109+
PROCEDURES																									
Bladder Biopsy f	X									X															
Cystoscopy ≠	X					X				X			X				X	X	X	X	X	X	X	X	X
Urine Cytology ≠ §	X					X				X			X				X	X	X	X	X	X	X	X	X
X-RAYS AND SCANS																									
ECG	X																								
CT or MRI	X																			X	¿				
TREATMENT																									
Atezolizumab α		X	X	X	X	X	X	X	X	X	X	X	X	X	X	X	X	X							
SPECIMEN SUBMISSION																									
Slides for Pathology Review (required) Δ	X Θ									X															X
FFPE tissue from TURBT/biopsy Π	X									X															X
Whole Blood £	X	X	X	X		X																			
Urine		X				X				X								X		X					
Urine Cytology Slide						X Ψ				X Ψ															

Click here for [Footnotes](#):

Footnotes for 9.1

- * If no treatment delays, treatment Cycles 5, 9, 13 and 17 coincide with disease assessment timepoints.
- € Bilirubin, SGOT [AST] or SGPT [ALT], creatinine, glucose, calcium, sodium, potassium, chloride and bicarbonate
- β ANC, platelets, hemoglobin
- £ Collect whole blood prior to drug infusion. See protocol [Section 15.0](#) for details.
- Δ Three H&E stained slides are REQUIRED to be submitted for central pathology review at any time a biopsy is performed for suspected recurrence. See protocol [Section 12.0](#) for details and shipping instructions.
- α Atezolizumab is given every 21 days. Vital signs should be monitored before, during, and after infusion. See [Section 7.2](#) for details.
- Σ To be performed within two weeks prior to registration
- ¥ To be performed more frequently if clinically indicated.
- ≠ Disease assessment will be performed every 3 months (12 weeks) for the first 2 years, then every 6 months (24 weeks) for Years 3-5 until HG recurrence or death. Disease assessment includes office cystoscopy and cytology A biopsy is required for suspicious cystoscopy findings or cytology results positive for malignancy.
- # Following a HIGH-GRADE recurrence within 5 years after registration, disease assessment is at discretion of treating investigator and the **S1605** Disease Assessment Form does not need to be submitted. However, the **S1605** Follow-up Form is still required for the full 5 year duration or death.
- f Bladder biopsy is REQUIRED for patients with any component of CIS at study entry (with or without concomitant Ta/T1 disease) within 7 days of Week 25 after registration, except where noted in [Section 7.3](#). All patients with suspicious cystoscopy findings or cytology positive for malignancy at any of the indicated diseases assessment times (or any other time, i.e. for cause) will undergo biopsy or TURBT. Patient should continue receiving atezolizumab while waiting for biopsy. Submit Pathology report for all biopsies performed, regardless of result.
- π Submit FFPE tissue any time a biopsy is performed for suspected recurrence of any type or persistent CIS.
- ι The CT or MRI scan must be performed at Week 73 for all patients who have not had a HG recurrence before that timepoint and scans must be submitted via AG Mednet. See [Section 15.2](#) for instructions.
- § Submit all cytology reports as a RAVE source document.
- Ω Follow-up safety assessments are required at 30 days and 90 days after the last dose of atezolizumab, regardless if patient has started a new cancer therapy. Report ALL toxicities, ALL Grades for first 30 days following last dose of protocol treatment on the last S1605 Adverse Event Form. Report ALL toxicities, ≥ Grade 3 for days 31-90 following last dose of protocol treatment on the **S1605** Late Effects Form. Amend original Late Effects form to add any additional toxicities ≥ Grade 3 experienced throughout remaining follow-up period.
- Ψ For all patients with CIS at study entry, one urine cytology slide is required for central pathology review. See [Section 12.0](#) for instructions.
- Θ Baseline histology used to diagnose disease for eligibility (from biopsy or TURBT), per [Section 5.1a](#).
- λ Baseline labs (except TSH) to be obtained within a window of 3 weeks.

Allowable windows

Treatment must begin within 7 calendar days of registration.

Allowable windows for scheduled disease assessments performed every 12 weeks is +/- 14 days, every 24 weeks is +/- 14 days. The window is to be calculated from the scheduled date of the procedure/assessment.

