		Anaphylaxis ³	
		Cytokine release syndrome ³	
		Immune system disorders - Other (systemic immune activation) ²	
INFECTIONS AND INFESTATIONS			

CLOSE

Adverse Events with Possible Relationship to Atezolizumab (MPDL3280A) (CTCAE 5.0 Term) [n= 3097]			Specific Protocol Exceptions to Expedited Reporting (SPEER)
Likely (>20%)	Less Likely (<=20%)	Rare but Serious (<3%)	
Infection ⁴			
INJURY, POISONING AND PROCEDURAL COMPLICATIONS			
	Infusion related reaction ³		
INVESTIGATIONS			
	Alanine aminotransferase increased ²		
	Alkaline phosphatase increased ²		
	Aspartate aminotransferase increased ²		
	Blood bilirubin increased ²		
	GGT increased ²		
	Lipase increased*		
		Platelet count decreased	
	Serum amylase increased*		
METABOLISM AND NUTRITION DISORDERS			
	Anorexia		Anorexia (Gr 2)
		Hyperglycemia ²	
	Hypokalemia		
	Hyponatremia		
MUSCULOSKELETAL AND CONNECTIVE TISSUE DISORDERS			
	Arthralgia ²		
	Back pain		
		Generalized muscle weakness	
	Myalgia		
		Myositis ²	
NERVOUS SYSTEM DISORDERS			
		Ataxia ²	
		Encephalopathy ²	
		Nervous system disorders - Other (encephalitis non-infective) ²	

CLOSE

Adverse Events with Possible Relationship to Atezolizumab (MPDL3280A) (CTCAE 5.0 Term) [n= 3097]			Specific Protocol Exceptions to Expedited Reporting (SPEER)
Likely (>20%)	Less Likely (<=20%)	Rare but Serious (<3%)	
		Guillain-Barre syndrome ²	
		Nervous system disorders - Other (meningitis non-infective) ²	
		Myasthenia gravis ²	
		Paresthesia ²	
		Peripheral motor neuropathy ²	
		Peripheral sensory neuropathy ²	
RENAL AND URINARY DISORDERS			
		Renal and urinary disorders - Other (nephritis) ²	
RESPIRATORY, THORACIC AND MEDIASTINAL DISORDERS			
	Cough		Cough (Gr 2)
	Dyspnea		
	Hypoxia		
	Nasal congestion		Nasal congestion (Gr 2)
		Pleural effusion ²	
		Pneumonitis ²	
SKIN AND SUBCUTANEOUS TISSUE DISORDERS			
		Bullous dermatitis ²	
	Pruritus		
	Rash acneiform		
	Rash maculo-papular		
	Skin and subcutaneous tissue disorders - Other (lichen planus) ²		

²Denotes adverse events that are < 3%.

¹ This table will be updated as the toxicity profile of the agent is revised. Updates will be distributed to all Principal Investigators at the time of revision. The current version can be obtained by contacting [contact]. Your name,

the name of the investigator, the protocol and the agent should be included in the e-mail.

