7.2 Treatment

Patients will receive intravenous atezolizumab (1200 mg) once every 21 days for a total of 17 doses (cycles). Atezolizumab treatment may be administered up to three days before or after the protocol-specified dose administration date, each 21 day cycle, due to administrative reasons. Atezolizumab treatment will be administered on an outpatient basis.

Agent	Dose	Route	Days	Interval	Notes
Atezolizumab	1200 mg	Intravenous over 60 minutes	1	q 21 days	for a maximum of 17 cycles

(51 weeks)

Atezolizumab administration instructions:

Administration of atezolizumab will be performed in a setting with emergency medical facilities and staff who are trained to monitor for and respond to medical emergencies.

Atezolizumab is administered as an intravenous infusion over 60 minutes. If the first infusion is tolerated, all subsequent infusions may be delivered over 30 minutes. Do not administer atezolizumab as an intravenous push or bolus. Vital signs (heart rate, respiratory rate, blood pressure, and temperature) should be monitored at the following timepoints during drug infusion:

- Before: Within 60 minutes of starting
- During: 15- 30 minutes after start
- After: At the end of infusion, within 30 minutes

No premedication is indicated for administration of Cycle 1 of atezolizumab. Patients who experience an infusion related reaction with Cycle 1 of atezolizumab may receive premedication with antihistamines or antipyretics/analgesics (e.g. acetaminophen) for subsequent infusions.

Premedication is not permitted for the first dose of atezolizumab. Premedication with antihistamines or antipyretics/analgesics (e.g., acetaminophen) may be administered for subsequent infusions at the discretion of the treating physician. The management of Infusion Related Reactions will be according to severity as follows:

- In the event that a patient experiences a Grade 1 Infusion Related Reaction during Cycle 1, the infusion rate should be reduced to half the rate being given at the time of event onset. Once the event has resolved, the investigator should wait for 30 minutes while delivering the infusion at the reduced rate. If tolerated, the infusion rate may then be increased to the original rate.

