8.2 General Adverse Event Management and Dose Modification Guidelines

Patients may temporarily suspend study treatment for up to 84 days (12 weeks) beyond the scheduled date of delayed infusion if study drug-related toxicity requiring dose suspension is experienced. If atezolizumab is held because of AEs for >84 days beyond the scheduled date of infusion, the patient will be discontinued from atezolizumab and will be followed for safety and efficacy as specified in this protocol. If the AE resolves within 84 days and the patient is receiving corticosteroid therapy for the event, atezolizumab may be held for longer than 84 days (up to 4 additional weeks) in order to allow tapering of the steroid dose to ≤ 10 mg oral prednisone or equivalent.

Dose interruptions for reasons other than toxicity, such as surgical procedures, may be allowed. The acceptable length of interruption will be at the discretion of the Study Chair.

Atezolizumab must be permanently discontinued if the patient experiences any of the following events, regardless of benefit:

- Grade 4 pneumonitis
- AST or ALT $>5\times$ ULN or total bilirubin $>3\times$ ULN
- Grade 4 diarrhea or colitis
- Grade 4 hypophysitis
- Any grade myasthenic syndrome/myasthenia gravis, Guillain-Barré or meningoencephalitis
- Grade 4 ocular inflammatory toxicity
- Grade 4 pancreatitis or any grade of recurrent pancreatitis
- Grade 4 rash
- Any grade myocarditis
- Grade 3 or 4 nephritis

Treatment may, under limited and compelling circumstances, be resumed in patients who have recovered from the following events, but only after consultation with the Study Chair:

- Grade 3 pneumonitis
- Grade 3 ocular inflammatory toxicity
- Grade 3 or 4 infusion-related reactions

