Any toxicities associated or possibly associated with atezolizumab treatment should be managed according to standard medical practice. Additional tests, such as autoimmune serology or biopsies, may be used to determine a possible immunogenic etiology. Although most immune-related adverse events (irAEs) observed with immunomodulatory agents have been mild and self-limiting, such events should be recognized early and treated promptly to avoid potential major complications (Di Giacomo et al., 2010). Discontinuation of atezolizumab may not have an immediate therapeutic effect, and there is no available antidote for atezolizumab. In severe cases, immune-related toxicities may be acutely managed with topical corticosteroids, systemic corticosteroids, or other immunosuppressive agents. The investigator should consider the benefit-risk balance prior to further administration of atezolizumab.

For detailed information regarding management of adverse events associated with atezolizumab, please refer to the most current version of the Atezolizumab Investigator's Brochure and the FDA product label.

The primary approach to Grade 1 to 2 irAEs is supportive and symptomatic care with continued treatment with atezolizumab; for higher-grade irAEs, atezolizumab should be withheld and oral and/or parenteral steroids administered. Recurrent Grade 2 irAEs may also mandate withholding atezolizumab or the use of steroids. Assessment of the benefit-risk balance should be made by the investigator, with consideration of the totality of information as it pertains to the nature of the toxicity and the degree of clinical benefit a given patient may be experiencing prior to further administration of atezolizumab. Atezolizumab should be permanently discontinued in patients with life-threatening irAEs.

Patients should be assessed clinically (including review of laboratory values) for toxicity prior to, during, and after each infusion. If unmanageable toxicity due to atezolizumab occurs at any time during the study, treatment with atezolizumab should be discontinued.

Systemic Immune Activation

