		
Refer patient to GI specialist for evaluation and confirmatory biopsy.
 
Initiate treatment with 1–2 mg/kg/day intravenous methylprednisolone or equivalent and convert to 1–2 mg/kg/day oral prednisone or equivalent upon improvement.
 
If event resolves to Grade 1 or better within 12 weeks, taper corticosteroids and resume atezolizumab according to the guidelines above.
 
Permanently discontinue atezolizumab if event does not resolve to Grade 1 or better within 12 weeks. Resumption of atezolizumab may be considered, after consultation with the Study Chair, in patients who are deriving benefit and have fully recovered from the immune-related event.

	Grade 4	
Permanently discontinue atezolizumab. Patient may not resume treatment, regardless of benefit.
 
Refer patient to GI specialist for evaluation and confirmation biopsy.
 
Initiate treatment with 1–2 mg/kg/day intravenous methylprednisolone or equivalent and convert to 1–2 mg/kg/day oral prednisone or equivalent upon improvement.
 
If event does not improve within 48 hours after initiating corticosteroids, consider adding an immunosuppressive agent.
 
If event resolves to Grade 1 or better, taper corticosteroids over ≥ 1 month.

Hepatotoxicity	Right upper-quadrant abdominal pain and/or unexplained nausea or vomiting	
Risk of immune-mediated hepatitis. LFTs should be performed immediately, and LFTs should be reviewed before administration of the next dose of study drug. For patients with elevated LFTs, concurrent medication, viral hepatitis, and toxic or neoplastic etiologies should be considered and addressed, as appropriate.
 
Symptoms of abdominal pain associated with elevations of amylase and lipase, suggestive of pancreatitis, have been associated with the administration of atezolizumab. The differential diagnosis of acute abdominal pain should also include pancreatitis, as described below.

AE Management and Dose Interruption Guidelines for Specific Toxicities		
Toxicity	Severity/ Duration	Management
	Grade 1 hepatic event	Continue atezolizumab. Monitor LFTs until values resolve to within normal limits.
	Grade 2 hepatic event, ≤5 days	Continue atezolizumab. Monitor LFTs more frequently until values resolve to baseline values.

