	Grade 2 hepatic event, >5 days	Hold atezolizumab. Initiate treatment with 1–2 mg/kg/day oral prednisone or equivalent. If event resolves to Grade 1 or better within 12 weeks, taper corticosteroids and resume atezolizumab according to the guidelines above. Permanently discontinue atezolizumab if event does not resolve to Grade 1 or better within 12 weeks.
	Grade 3 or 4 hepatic event	Permanently discontinue atezolizumab. Consider patient referral to GI specialist for evaluation and liver biopsy to establish etiology of hepatic injury. Initiate treatment with 1–2 mg/kg/day oral prednisone or equivalent. If event does not improve within 48 hours after initiating corticosteroids, consider adding an immunosuppressive agent. If event resolves to Grade 1 or better, taper corticosteroids over ≥1 month.
Hyperglycemia	Grade 1 or 2	Continue atezolizumab. Initiate treatment with insulin if needed. Monitor for glucose control.
	Grade 3 or 4	Hold atezolizumab. Initiate treatment with insulin. Monitor for glucose control. Resume atezolizumab when symptoms resolve and glucose levels are stable.
Hyperthyroidism	Grade 1 (asymptomatic)	TSH ≥ 0.1 mU/L and < 0.5 mU/L: Continue atezolizumab. Monitor TSH every 4 weeks. TSH < 0.1 mU/L:

AE Management and Dose Interruption Guidelines for Specific Toxicities		
Toxicity	Severity/ Duration	Management
		Follow guidelines for symptomatic hyperthyroidism.
	Grade 2+ (symptomatic)	
Hold atezolizumab.
 
Initiate treatment with anti-thyroid drug such as methimazole or carbimazole as needed.
 
Consider patient referral to endocrinologist.
 
Resume atezolizumab when symptoms are controlled and thyroid function is improving.
 
Permanently discontinue atezolizumab for life-threatening immune-related hyperthyroidism.

Hypothyroidism	Grade 1 (asymptomatic)	
Continue atezolizumab.
 
Start thyroid-replacement hormone.
 
Monitor TSH weekly.

	Grades 2+ (symptomatic)	
Hold atezolizumab.
 
Start thyroid-replacement hormone. Consider referral to an endocrinologist.
 
Monitor TSH weekly.
 
Restart atezolizumab when symptoms are controlled and thyroid function is improving.

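### The Section 9.1 chemistry footnote requires only one transaminase, while the Section 8.2 stop and the Section 16.1f reports act on either, leaving a narrow safety-monitoring gap

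*Combined protocol and SAP*

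**What the plan says.** **Test list.** In the Section 9.1 calendar, the CMP/Serum Chemistry row is marked at baseline and at every treatment visit from week 1 to week 49. Its footnote gives the content as "Bilirubin, SGOT [AST] or SGPT [ALT], creatinine, glucose, calcium, sodium, potassium, chloride and bicarbonate".

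**Stop rule.** Section 8.2 lists events after which atezolizumab must be stopped for good, whatever the benefit to the patient. One of them is "AST or ALT $>5\times$ ULN or total bilirubin $>3\times$ ULN".

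**Expedited reporting.** The list of adverse events of special interest in Section 16.1f has two separate entries, ALT above 10 x ULN and AST above 10 x ULN. Its Hy's Law entry uses ALT or AST above 3 x ULN, combined with total bilirubin above 2 x ULN or with clinical jaundice.

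**Safeguards.**
- In the Section 8.3 hepatotoxicity table, right upper-quadrant pain or unexplained nausea or vomiting means that "LFTs should be performed immediately, and LFTs should be reviewed before administration of the next dose of study drug".
- The same table requires LFT monitoring for a Grade 1 hepatic event and more frequent monitoring for a Grade 2 event of up to five days. A longer Grade 2 event means a hold and steroids.
- Section 8.2 adds: "Patients should be assessed clinically (including review of laboratory values) for toxicity prior to, during, and after each infusion".

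**The concern.** The word 'or' does different work in the two places. In a list of tests, it lets the site choose one. In a trigger, it means that either result is enough, so the rule can be applied in full only when both results are known. The panel that feeds the hepatic rules therefore does not guarantee the data those rules need.

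Patient safety is at stake. A fully compliant site could continue dosing through a rise that the protocol says must end treatment, and could fail to send an expedited report, because the enzyme concerned was never requested. The efficacy analyses are not involved.

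**Working it through.** No sample size, power or error rate is involved, so the check compares the sections directly, with one count.

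1. **How often one enzyme is enough.** Visits run from week 1 to week 49 in steps of 3: (49 - 1)/3 + 1 = 17, which matches the 17 doses in Section 7.2. Adding baseline gives 1 + 17 = 18 scheduled chemistries, each met by one transaminase.

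2. **Longest stretch without a scheduled value for the other enzyme.** 17 cycles x 21 days = 357 days, and 357/7 = 51 weeks. This is simply the treatment length given in Section 7.2.

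3. **Whether both enzymes are scheduled elsewhere.** No visible section requires both routinely. The two are listed together as tests only in the Section 8.2 work-up for suspected systemic immune activation, which starts from a sepsis-like syndrome.

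4. **What each safeguard catches.** Take a site that runs only AST and a patient whose ALT rises above 5 x ULN. The argument is the same with the enzymes exchanged.
   - *AST also rises to Grade 1 or 2:* Section 8.3 calls for LFT monitoring, so ALT should then be seen. The table does not itemise LFTs; I read the term as covering both enzymes.
   - *Bilirubin rises:* it is in every panel and has its own stop in Section 8.2 at more than 3 x ULN.
   - *The listed abdominal symptoms appear:* Section 8.3 calls for immediate LFTs.
   - *Laboratory review around each infusion:* this can use only results that were obtained, so it does not help.

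5. **What remains.** A trigger is missed only when all three conditions hold together: the measured enzyme is ungraded, bilirubin is normal, and there are no prompting symptoms. In that case the triggers that can be missed are the 5 x ULN stop and the 10 x ULN report. The Hy's Law entry is also worded on either enzyme, but it needs raised bilirubin or jaundice as well, so normal bilirubin without jaundice would not meet it.

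**The case against.** The strongest reply is that AST or ALT is the protocol's convention throughout (entry criterion 5.4c, the panel, the stop rule and Hy's Law), so a site with one enzyme applies each rule to the value it has. The Section 16.1f list says what to report once seen; it is not a testing schedule. The row is headed CMP, so many sites will obtain both enzymes anyway. Sections 8.2 and 8.3 also refer sites to the Investigator's Brochure for hepatitis management, and 8.2 refers them to the label; monitoring advice may sit there.

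Part of this stands. The gap is probably uncommon in practice, and the Brochure and label could not be checked. But the convention argument fails. The stop depends on the patient's enzyme levels, not on which test was ordered. Neither the row heading nor the Brochure changes what the footnote requires.

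Four stronger readings are tempting, and the documents do not support them:
- **That the Section 8.3 table is itself an either-enzyme rule.** It names no enzyme. Its Grade 3 or 4 row, "Permanently discontinue atezolizumab. Consider patient referral to GI specialist for evaluation and liver biopsy to establish etiology of hepatic injury", refers to a hepatic event.
- **That the adverse event list in Section 3.1 implies a duty to measure both.** It does list "Alanine aminotransferase increased" and "Aspartate aminotransferase increased" separately. It also lists alkaline phosphatase, GGT, lipase and amylase, none of which is in the panel.
- **That 357 days measures undetected liver injury.** It is treatment length. Nothing in the documents shows how often one enzyme passes 5 x ULN while the other stays ungraded, or how many sites run only one.
- **That eligibility criterion 5.4c needs the same edit.** That is a separate entry question. Tightening it would exclude some patients and would not improve monitoring on treatment.

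**Conclusion.** The mismatch is real and minor. One transaminase satisfies the calendar at all 18 chemistries, while the mandatory stop and the expedited reports act on either. A compliant single-enzyme site can miss a trigger only in the three-condition case described above. CR, EFS and the trial's error rates are unaffected.

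The conclusion assumes that the footnote sets the required content of the row, that LFTs in Section 8.3 means both enzymes, and that the unseen Brochure and label do not separately require both at each cycle. If a site read LFTs as a repeat of its single enzyme, the Section 8.3 safeguards would catch less. If the Brochure does require both, the remaining problem is an inconsistent footnote. The frequency of missed triggers cannot be estimated from the documents.

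**What to change.** In the Section 9.1 footnote, replace the choice of enzyme with SGOT [AST] and SGPT [ALT], applying at baseline and at every scheduled chemistry. This is a one-word change. The blood is already drawn for the row, so the cost is at most one added analyte at sites that do not run a full CMP. Leave criterion 5.4c as it is.

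If no patients remain on treatment, the per-cycle laboratory values requested in Section 14.4q could show where only one enzyme was run, provided that the form records each separately (its fields are not shown). They cannot recover an enzyme that was never measured.
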